TITLE: Celecoxib for Thyroid Eye Disease

NCT: 02845336

PI: [name]

DATE: January 21, 2017

Date: January 21, 2017 Principal Investigator: [name] Application Number: IRB00094787

JHM IRB - eForm A – Protocol

- Use the section headings to write the JHM IRB eForm A, inserting the appropriate material in each. If a section is not applicable, leave heading in and insert N/A.
- When submitting JHM IRB eForm A (new or revised), enter the date submitted to the field at the top of JHM IRB eForm A.

1. Abstract

- Thyroid eye disease (TED) is an autoimmume disorder in which autoantibodies against the TSH receptor attack orbital tissues, resulting in characteristic changes in eyelid position, globe position in the orbit, extraocular muscle balance, and optic nerve function. TED is a potentially blinding disease, and current treatments largely consist of nonspecific reduction of inflammation using corticosteroids or radiation therapy. The former treatment has significant morbidity, while the latter is controversial. Rituximab, which depletes CD20+ cells, has been used recently in severe disease but has evoked concern because of its cost and potential morbidity. Regardless of treatment, once TED progresses from its inflammatory phase to a more fibrotic, resolution phase, the orbital changes become fixed and can be modified only by surgery. We intend to use celecoxib (Celebrex), a non-steroidal anti-inflammatory drug approved by the Food and Drug Administration (FDA) for the treatment of pain, osteoarthritis, rheumatoid arthritis, and ankylosing spondylitis, as a treatment for active TED. In vitro data have shown that transformation of orbital fibroblasts into adipocytes is mediated by cyclooxygenase-2 (COX-2) via the PPAR-gamma pathway, and a single case report suggests that COX-2 inhibition can improve TED in the acute phase. Thus, we intend to evaluate the efficacy of COX-2 inhibition in the treatment of active TED and its ability to improve both the acute inflammatory signs and more permanent fibrotic changes of quiescent disease. We will enroll patients with active TED and treat them for 3 months (a characteristic period of disease activity) and compare this to standard treatments for mild TED (observation with only over the counter interventions such as lubrication with artificial tears) to assess efficacy.
- 2. **Objectives** (include all primary and secondary objectives)
 - Study the effectiveness of celecoxib (Celebrex) in the reduction of orbital inflammation in patients with thyroid eye disease.
 - Primary outcome- reduction of clinical activity (by Clinical Activity Score (CAS) and VISA score (Vision, Inflammation, Strabismus, Appearance))
 - Secondary outcomes- improvement in proptosis, strabismus, and eyelid retraction, and TED quality of life questionnaire

3. Background

Date: January 21, 2017 Principal Investigator: [name] Application Number: IRB00094787

- Thyroid eye disease (TED) occurs in up to 50% of patients with Graves disease and to a lesser 0 extent in Hashimoto thyroiditis. Autoantibodies to the TSH receptor [thyroid stimulating immunoglobulin (TSI) and TSH receptor antibody (TSHR Ab)] have cross-reactivity with similar antigens on the surface of orbital cell membranes. The basic pathogenesis of TED involves a cell-mediated inflammatory process that attacks orbital soft tissues, including adipocytes, fibroblasts, and extraocular muscle. Their binding results in recruitment of T-cells and monocytes (and B-cells to a lesser extent) and secretion of inflammatory cytokines. After an acute inflammatory phase, a chronic condition results from persistent tissue changes including extraocular muscle fibrosis and fat hypertrophy. Vision problems result when adipocyte proliferation leads to proptosis and corneal exposure, and extraocular muscle enlargement in addition to adipogenesis can cause compressive optic neuropathy. Proptosis is also disfiguring and can be remedied only by surgery after the inflammatory phase resolves; this can take 1-2 years without any medical intervention. Chronic TED responds only to surgical correction, and treatment in the acute phase can reduce morbidity. Current treatments of active TED involve nonspecific anti-inflammatory medications such as corticosteroids (with the attendant side effects) and orbital radiotherapy (controversial because of limited data supporting efficacy and theoretic risk of secondary malignancy). Recently, rituximab has been used in severe cases, but its expense and side effect profile have limited its utility.
- In addition to cytokines, activated T-cells produce ligands for peroxisome proliferator activated receptor (PPAR) gamma. These ligands include prostaglandins created via the cyclooxeganse-2 (COX-2) pathway. PPAR-gamma activation has been implicated in systemic adipogenesis in patients taking thiazolidinedione drugs for glycemic control, and *in vitro* studies of cultured orbital fibroblasts have shown that exposing cells to PPAR-gamma ligands such as specific prostaglandin analogues results in transformation of fibroblasts into adipocytes. This effect is more robust with TED fibroblasts than in cells isolated from control patients. Inhibiting the PPAR-gamma pathway *in vitro* with a selective COX-2 inhibitor blocks fibroblast transformation. A single case report in the literature also supports the possible *in vivo* efficacy of COX-2 inhibition in active TED.
- Based on these *in vitro* and *in vivo* findings, we propose to treat a cohort of patients with active TED using a selective COX-2 inhibitor, celecoxib (Celebrex), and to compare these patients to an observational control group. We hypothesize that celecoxib will reduce the severity of disease and/or prevent progression to proptosis, diplopia, and corneal exposure or compressive optic neuropathy. We will assess the effect of the treatment using validated clinical scoring tools, including the Clinical Activity Scale (CAS) from the European Graves Orbitopathy Group (EUGOGO) and the VISA (vision, inflammation, strabismus, appearance) scale of the International Thyroid Eye Disease Study (ITEDS) group. We will also use a validated Graves ophthalmopathy quality of life survey as a secondary outcome measure. Outcomes will be assessed at timepoints noted below with a 3-month period of treatment and follow-up for 1 year.

4. Study Procedures

- Patients will be recruited from the Wilmer Eye Institute practices of the investigators.
- The exam will include a thorough history including a list a medications, health conditions previous surgeries and medical allergies (standard of care).
- The complete eye examination will measure visual acuity, eye movements (sensorimotor exam), visual fields, proptosis, pupil function, anterior segment evaluation, and lastly dilated fundus

exam to evaluate the potential subject's optic nerve. Photographs (external, eye movements, optic nerve) may be taken as needed. This eye examination is standard of care on any thyroid eye disease patient. Findings from the eye exam will be used to determine a CAS and VISA score. The CAS takes into account 7 manifestations (spontaneous retrobulbar pain, pain with eye movement, eyelid erythema, eyelid edema, conjunctival injection, chemosis, and caruncular swelling) with 1 point assigned for each positive finding. The VISA score ranges from 0-16 based on findings related to inflammation, strabismus, and eyelid changes and proptosis (appearance). Both scales were developed to assess features of active disease that might change with treatment.

- Study subjects will be randomly assigned to observation with no prescription treatment, or treatment with oral celecoxib 100 mg twice daily for 3 months. Patients will have a full clinical exam at baseline, 1 month, 3 months, 6 months, and 12 months, with additional clinical visits more frequently if indicated by disease course/activity. The proposed frequency of clinic visits is within standard of care for newly diagnosed active-phase TED.
- For those subjects randomized to the treatment group, baseline blood testing for blood counts, renal and hepatic function (BUN, Cr, AST, ALT, total bilirubin) will be obtained prior to starting the drug. Testing will be performed by a standard clinical laboratory and billed to insurance. Testing will be repeated at 1mo and 3mo after randomization/initiation of therapy for those receiving celecoxib. Abnormal BUN or creatinine (outside normal range) on lab testing or any previous/current kidney disease will be the criteria for labeling a patient as having impaired renal function. Abnormal liver enzymes (AST, ALT, bilirubin outside normal range) or previous/current liver disease will determine whether a patient is labeled as having impaired hepatic function. Monthly phone interviews also will be conducted by physician study team members to determine if other side effects, such as edema, may be occurring. Subjects will be asked specifically about peripheral swelling, any blood in urine or skin discoloration, or changes in exercise tolerance. Positive responses will trigger an unscheduled visit with the PI or co-investigator MD. Patients will be cautioned not to take additional NSAID medications while on Celecoxib, as this may increase the chance for adverse effects.
- Outcomes: The primary study outcome is reduction of clinical activity of TED, as determined by both the CAS and VISA scores. We will use both scales because there is currently disagreement as to which scale serves as a better overall assessment tool. Secondary outcome measures will include reduction of specific aspects of TED, including proptosis, diplopia, and eyelid retraction, as well as a validated TED-specific quality of life survey. These elements are captured in part by the 2 scales but also will be evaluated separately. Comparison of our primary and secondary outcomes between the treatment and control groups and with published studies of steroid treatment for TED may provide us with an indication of the relative efficacy of celecoxib treatment and whether further study is warranted. Treatment safety also will be assessed, and adverse events recorded. A recent prospective study of intravenous corticosteroid dosing for TED reported major adverse events in 10/159 (6.3%) of subjects and minor adverse events such as gastric distress, mild BP increase not requiring medication, and local skin reactions in about 25% of subjects. We anticipate a lesser incidence of minor or major adverse events based on the side effect profile of celecoxib in patients without co-morbidities placing them at higher risk (most TED patients are young and otherwise healthy). Occurrence of adverse events at a rate

greater than what has been reported for intravenous corticosteroid (an accepted method of TED treatment) would suggest that risk of celecoxib treatment exceeds any benefit.

- Biospecimens will be collected in this study, to include urine for a pregnancy test for female patients of childbearing age to determine eligibility, as well as blood as noted above that will be drawn by the clinical lab.
- Study length: Subjects will be followed for 12 months.
- Safety monitoring: As noted, baseline blood testing and phone surveillance will be performed. If abnormal results are found during drug treatment, then subjects will be advised to stop the medication and will be examined by the PI or other MD investigator. Adverse events will be reported to the IRB per institutional policy.
- Subjects may be taken out of the study if:
 - Staying in the study would be harmful.
 - Treatment required is not allowed in the study.
 - Those that fail to follow instructions.
 - Subjects become pregnant.
 - The study is cancelled.
 - There may be other reasons to take subjects out of the study that we do not know at this time.

5. Inclusion/Exclusion Criteria

Eligibility criteria:

- *Recent diagnosis of thyroid eye disease (within the past 6 months)*
- Have ocular symptoms or signs of TED with a CAS score of at least 3
- Ages 18-80 years

Exclusion criteria:

- Pregnancy
- Previous treatment with corticosteroid for TED for >2wks
- Previous treatment with orbital radiation for TED
- Impaired renal function
- Impaired hepatic function
- *Treatment with antihypertensive medications except beta-blockers*
- History of congestive heart failure, cardiac valvular disease, or coronary artery disease
- Allergy to NSAID or previous adverse reaction (ie. GI bleeding)
- Vision loss due to compressive optic neuropathy

Target 40 participants will be enrolled in this study.

6. Drugs/ Substances/ Devices

Celecoxib (Celebrex) is a non-steroidal anti-inflammatory drug approved by the Food and Drug Administration (FDA) for the treatment of pain, osteoarthritis, rheumatoid arthritis, and ankylosing spondylitis. We will be using the recommended dosage of 100 mg twice a day over the course of 3 months. Celecoxib for TED is an off-label usage.

7. Study Statistics

The primary study outcome is reduction of clinical activity of TED, as determined by both the CAS and VISA scores. We will use both scales because there is currently disagreement as to which scale serves as a better overall assessment tool. Secondary outcome measures will include reduction of specific aspects of TED, including proptosis, diplopia, and eyelid retraction. These elements are captured in part by the 2 scales but also will be evaluated separately. Change in quality of life will be measured by a validated questionnaire as another secondary outcome measure. Comparison of our primary outcomes between treatment and control groups will provide us with an indication of the relative efficacy of celecoxib treatment. Treatment safety also will be assessed, and adverse events recorded. A recent prospective study of intravenous corticosteroid dosing for TRO reported major adverse events in 10/159 (6.3%) of subjects and minor adverse events such as gastric distress, mild BP increase not requiring medication, and local skin reactions in about 25% of subjects. We anticipate a lesser incidence of minor or major adverse events based on the side effect profile of celecoxib in patients without co-morbidities placing them at higher risk (most TED patients are young and otherwise healthy). Occurrence of adverse events at a rate greater than what has been reported for intravenous corticosteroid (an accepted method of TED treatment) would suggest that risk of celecoxib treatment exceeds any benefit. Observation of adverse events in excess of this rate during the treatment phase would require review, and consideration of early study termination. The changes in either the CAS or VISA score will be compared between the celecoxib and observation groups to determine whether a trend or significant difference can be found.

8. Risks

The study procedures, apart from the proposed treatment, carry no risk beyond that of standard clinical care. Celecoxib has well-described risks especially in certain patient populations, who will be excluded from this study as noted. Below is an enumeration of risks copied from the package insert:

- **Cardiovascular warning:** All prescription NSAIDs, like CELEBREX, ibuprofen, naproxen, and meloxicam have the same cardiovascular warning. They may all increase the chance of heart attack or stroke that can lead to death. This chance increases if you have heart disease or risk factors for it, such as high blood pressure or when NSAIDs are taken for long periods. Congestive heart failure and peripheral edema has also occurred in some patients has also been noted.
- CELEBREX should not be used right before or after certain heart surgeries.
- Stomach and intestine risk: All prescription NSAIDs have the same warning for serious stomach and intestine problems: They may cause ulcers and bleeding, which can occur without warning and may cause death.
- **Renal warning:** Long term use of NSAIDs, like CELEBREX, have resulted in renal papillary necrosis. Patients at risk are those with impaired renal function, heart failure, liver dysfunction, those taking diuretics, ACE inhibitors, and angiotension II inhibitors.

Date: January 21, 2017 Principal Investigator: [name] Application Number: IRB00094787

• Serious skin and allergic reactions can occur with CELEBREX. CELEBREX shold not be taken if one has had an asthma attack, hives, or other allergies to aspirin, other NSAIDs, or certain drugs called sulfonamides.

Risks of corticosteroid treatment are noted in section 7 with at least 25% of patients experiencing a minor or major adverse event. Orbital radiotherapy carries theoretic risk of ocular radiation toxicity (cataract formation, radiation retinopathy or optic neuropathy) and second malignancy occurrence, but the actual rate of such events is not known. Untreated, some patients with TED may have spontaneous improvement while others will progress to more severe manifestations. Increased disease activity at presentation is a predictor for progression, and we thus are including only subjects with clinical activity that may put them at risk for such changes. Treatment is effective only during the active phase of TED, and observation may result in irreversible proptosis or strabismus requiring subsequent surgery.

9. Benefits

The major benefit of the study is anticipated to be reduction of TED severity as measured by clinical activity assessment.

10. Payment and Remuneration

Subjects will not be compensated for participation.

11. Costs

Subjects will receive a separate Insurance and Research Participant Financial Responsibility Information Sheet (Sheet).

This Sheet will give subjects the following information:

- The drugs that are part of this research will be paid for by their insurance
- The required laboratory testing will be paid for by their insurance
- The standard eye examination, procedures and tests that will be performed will be billed to the subject and/or their health insurer. Subjects with health insurance will be responsible for any copays or deductibles not covered by their insurance. All planned visits with standard testing are consistent with standard of care and will be charged to insurance as usual.

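### The observation arm is justified for mild TED, but entry is not confined to mild disease, and taking out subjects who need other treatment is likely to bias the comparison against celecoxib

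*Combined protocol and SAP*

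**What the plan says.** **Control rationale.** Section 1 (Abstract) describes the population by activity: "We will enroll patients with active TED and treat them for 3 months". The same sentence then describes the comparator by severity: the trial will "compare this to standard treatments for mild TED", which it takes to mean observation plus non-prescription measures such as artificial tears. This is the only place where the disease under study is linked to the word mild. Section 4 (Study Procedures) puts the comparator into effect: "Study subjects will be randomly assigned to observation with no prescription treatment".

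**Entry.** Section 5 (Inclusion/Exclusion Criteria) asks for a diagnosis within 6 months, age 18-80, and: "Have ocular symptoms or signs of TED with a CAS score of at least 3". It excludes visual loss from optic nerve compression. It sets no limit on proptosis, diplopia, corneal exposure or lid retraction.

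**Risk.** Section 8 (Risks) says that higher activity at presentation predicts progression, and continues: "we thus are including only subjects with clinical activity that may put them at risk for such changes". It also says that treatment works only in the active phase and that "observation may result in irreversible proptosis or strabismus requiring subsequent surgery".

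**Leaving the study.** Among the reasons in Section 4 for which a subject may be taken out is: "Treatment required is not allowed in the study". Section 4 does not list which treatments are disallowed or what would trigger removal. Section 7 (Study Statistics) names no analysis population and gives no rule for subjects who leave or start other treatment.

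**The concern.** The comparator is justified for one group and the entry criteria admit a wider one. A subject beyond mild disease can be randomised to observation on a rationale that the protocol gives only for mild disease. Section 3 (Background) describes current treatment of active TED as corticosteroids and orbital radiotherapy and does not mention observation there.

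Two things are at stake. The first is the protocol's own account of risk: it warns of irreversible change under observation but does not tie that warning to the severity range on which the control rationale rests. The second is bias. Subjects who worsen are the ones most likely to need another treatment. If celecoxib has any benefit, more of them will be in the observation arm. The control arm also takes no prescription drug and no masking is described, so the decision to start other treatment may itself depend on the arm. If these subjects leave and only those who remain are compared, the controls look better than they were.

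**Working it through.** **Step 1: does entry match the rationale?** This is a comparison of text, and the plan has no figure to reproduce.

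| Question | Where | Finding |
|---|---|---|
| For whom is observation called standard? | Section 1 | Mild TED |
| Is mild disease required at entry? | Section 5 | No |
| Does the CAS threshold limit severity? | Sections 4 and 5 | No. CAS counts 7 inflammatory findings, and 3 is a minimum with no maximum |
| Is any severity-type feature excluded? | Section 5 | One: visual loss from optic nerve compression |
| Does the steroid exclusion limit severity? | Section 5 | Not directly. It concerns more than 2 weeks of earlier treatment |
| How does Section 8 describe those included? | Section 8 | By activity and risk of progression, not by severity at entry |

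The criteria therefore allow mild disease but do not ensure it.

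**Step 2: which way does removal push the result?** Let higher values mean more improvement. Removing the lowest values from the control arm raises the control mean and shrinks the difference in favour of celecoxib.

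**Step 3: illustration of size.** The documents give 40 participants and no SD, effect size, power, allocation ratio or dropout rate. Everything else here is assumed: 20 per arm, a normal outcome with SD 1, a two-sided 5% t-test, and analysis of remaining subjects only. The effect detectable with 80% power is then 0.909 SD.

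When the worst fraction f of a standard normal is removed, the mean rises by φ(z₁₋f)/(1−f):

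| Worst controls removed | f | Rise in control mean (SD) | Difference left (SD) |
|---|---|---|---|
| 2 of 20 | 10% | 0.195 | 0.909 − 0.195 = 0.714 |
| 4 of 20 | 20% | 0.350 | 0.909 − 0.350 = 0.559 |
| 6 of 20 | 30% | 0.497 | 0.909 − 0.497 = 0.412 |

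Putting these differences into the power formula with the SD held at 1 and 20 per arm gives about 60%, 41% and 25%. That is too pessimistic, because removing a tail also reduces the control SD. Simulating the removal from samples of 20, with the reduced SD and the smaller arm both allowed for, gives (to within about one percentage point):

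| Worst controls removed | No celecoxib subject removed | Half as many of the worst celecoxib subjects removed |
|---|---|---|
| 0 | 80% | 80% |
| 2 | 64% | 76% |
| 4 | 46% | 71% |
| 6 | 28% | 65% |

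The gap between the last two columns shows that the loss depends mainly on how uneven removal is between the arms.

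**The case against.** The strongest reply is that activity and severity are different things. A CAS of 3 or more does not make disease more than mild. Section 8 speaks of activity and future risk. Section 3 hopes to prevent progression to proptosis, diplopia and corneal exposure, which is compatible with entry before those changes, and Section 5 requires a recent diagnosis. All of this stands. A reader might infer that the control is wrong for the enrolled population, or that eligibility has no severity limit at all. The documents support neither: they leave the fit unassured, and visual loss from optic nerve compression is excluded.

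A reader might also infer that worsening controls are simply left alone. They are not. Section 4 schedules full examinations at baseline and at 1, 3, 6 and 12 months for both arms, adds visits when disease course calls for them, and allows removal if staying would be harmful. Section 8 states the risk of observation openly. The consent pages are not available, so what subjects are told cannot be judged.

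Nor is the study population undefined. Section 5 defines it; what is missing is a severity range. Severity features are already examined at baseline (proptosis, eye movements and the findings that feed VISA), so no new measurement is needed.

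On bias, the removal list applies to both arms, removal is discretionary, and no section says that data from subjects taken out are discarded. Losing such subjects would also be a problem under a perfect severity criterion. These points limit the size of the effect and make the power figures an illustration. They do not remove the risk, because no section says that such subjects are followed or how they are analysed.

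**Conclusion.** The point holds in this form. Sections 1, 5 and 8 do not agree on whom the observation control is meant for, and the entry criteria do not ensure that its rationale fits those enrolled. Which clinical position is right is for the sponsor and the IRB.

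The statistical consequence comes through the Section 4 removal provision. If it is followed, and only subjects who remain are compared, it is likely to favour the observation arm. The error to expect is a missed or understated benefit of celecoxib; the documents give no ground for reading it as a route to a false claim of benefit.

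The size is unknown. In the illustration, power falls from 80% to between 64% and 28% if only controls are lost, and to between 76% and 65% if half as many of the worst celecoxib subjects also leave. These ranges rest on assumed equal allocation, effect size, normal outcome and loss fractions, and on removal of exactly the worst subjects, which is a bounding case. The finding on the text does not depend on them. The change is worth making because it is cheap and the trial is small.

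**What to change.** 1. **Reconcile Sections 1, 5 and 8.** Either Section 5 carries the severity range on which the control rationale depends, or Section 1 restates the rationale for the population that Section 5 admits. The sponsor and IRB choose.
2. **Separate leaving treatment from leaving the study.** Amend the removal provision in Section 4 so that a subject who starts other TED treatment, and stops study treatment if that is required, stays in the scheduled 1, 3, 6 and 12 month visits. Clinical decisions on treatment stay with the investigators.
3. **State the analysis in Section 7.** Analyse all subjects in the arm to which they were randomised, including outcomes after other treatment, and report starts of other TED treatment by arm with their timing.
4. **Describe baseline severity by arm** from the proptosis, motility and VISA data already collected.

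The cost is protocol wording and the effort of retaining a few more subjects at visits already scheduled. If the sponsor chooses to add a severity range, the eligible pool may become somewhat narrower. The statistical price is that outcomes recorded after other treatment dilute the contrast somewhat, so the comparison becomes one of starting with celecoxib against starting with observation. Reporting other treatment by arm lets the reader see how much dilution to expect.

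### Two of the seven CAS points are pain and celecoxib is a pain drug; Section 7 should add a supportive five-sign CAS comparison so that an on-drug CAS difference can be read correctly

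*Combined protocol and SAP*

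**What the plan says.** All references are to the combined protocol and SAP.

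- **Objective (Section 2):** "Study the effectiveness of celecoxib (Celebrex) in the reduction of orbital inflammation". The primary outcome beneath it is reduction of clinical activity by CAS and VISA.
- **Score (Section 4):** "The CAS takes into account 7 manifestations (spontaneous retrobulbar pain, pain with eye movement", followed by eyelid erythema, eyelid edema, conjunctival injection, chemosis and caruncular swelling, "with 1 point assigned for each positive finding". VISA is described as running from 0 to 16 over inflammation, strabismus and appearance. Its items are not listed and none is named as pain.
- **Drug (Sections 1 and 6):** an NSAID "approved by the Food and Drug Administration (FDA) for the treatment of pain", among other uses.
- **Arms (Section 4):** "Study subjects will be randomly assigned to observation with no prescription treatment, or treatment with oral celecoxib", the latter for 3 months. No placebo is described.
- **Visits (Section 4):** "Patients will have a full clinical exam at baseline, 1 month, 3 months, 6 months, and 12 months".
- **Entry (Section 5):** "Have ocular symptoms or signs of TED with a CAS score of at least 3".
- **Analysis (Section 7):** "The changes in either the CAS or VISA score will be compared between the celecoxib and observation groups". Proptosis, diplopia, eyelid retraction and quality of life are secondary outcomes. No item-level or signs-only CAS analysis is planned.
- **Analgesics:** Section 4 cautions subjects on celecoxib against additional NSAIDs. Section 1 describes control care as over-the-counter measures, with artificial tears as the example, and does not say whether analgesics are included.

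**The concern.** The months 1 and 3 examinations fall during or at the end of the dosing period. A drug that relieves pain can take up to two points off CAS at those visits while the five signs stay as they were, and the observed controls receive no matching analgesic. A between-arm difference in total CAS could then come from pain relief, from less orbital inflammation, or from both.

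Section 5 of the page order aside, the plan ties this comparison to a decision: the outcomes text in Section 4 says the results may indicate relative efficacy and whether further study is warranted. The hypothesised mechanism in Section 3 is COX-2 and PPAR-gamma mediated transformation of orbital fibroblasts, not analgesia. An on-drug CAS difference carried mainly by the pain items would be weaker support for that hypothesis than one seen in the signs, and the planned total does not separate the two.

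**Working it through.** The plan gives no power calculation, SD, pain prevalence or allocation ratio, so there is no figure of its own to reproduce. Step 1 uses the documents alone. Steps 2 and 3 rest on assumed inputs.

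**1. What the scoring allows.** Seven binary items give 2^7 = 128 patterns.
- CAS of 3 or more: 35 + 35 + 21 + 7 + 1 = 99 patterns.
- Of these, patterns with no pain item need at least 3 of 5 signs: 10 + 5 + 1 = 16. So 99 - 16 = 83 include pain.
- Both pain items plus at least one sign: 2^5 - 1 = 31.
- Fewer than 3 signs: one pain item with 2 signs (2 x 10 = 20) plus two pain items with 1 or 2 signs (5 + 10 = 15), which is 35. Clearing pain alone takes these 35 below the entry threshold.

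Pain is 2/7 (29%) of the maximum score and can be 2/3 of the points at CAS 3. These are counts of patterns, not prevalences.

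**2. How often pain relief alone would make the CAS test significant.** Assumed: 20 per arm, two-sided 5%, SD of CAS change 1.5 or 2.0, no effect on signs. Mean shift = 2 items x baseline prevalence p of each x net relief r over control. Noncentrality = shift / (SD x sqrt(2/20)), 38 df.

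| p, r | Shift | SD 1.5 | SD 2.0 |
|---|---|---|---|
| 0.3, 0.3 | 0.18 | 6.6% | 5.9% |
| 0.5, 0.5 | 0.50 | 17.7% | 12.0% |
| 1.0, 0.5 | 1.00 | 53.8% | 33.8% |

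The last row needs every participant to have both pain items at baseline, so it is an upper scenario for prevalence. The SD matters too: at SD 1.0 the 0.50 shift has the same standardised size (0.5) as 1.00 at SD 2.0, hence 33.8%.

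**3. What a five-sign comparison could show.** With complete item scores, CAS difference = five-sign difference + pain-item difference, exactly. Assume an SD of 0.75 for change in the two pain items together and a pain-sign correlation of 0 or 0.3. Solving SD_CAS^2 = 0.75^2 + s^2 + 2 x corr x 0.75 x s for the sign SD s gives the first row below. The 95% CI half-width is 2.024 x SD x sqrt(2/20).

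| | CAS SD 1.5 (corr 0 / 0.3) | CAS SD 2.0 (corr 0 / 0.3) |
|---|---|---|
| Sign SD | 1.30 / 1.09 | 1.85 / 1.64 |
| Half-width, signs | 0.83 / 0.70 | 1.19 / 1.05 |
| Half-width, CAS | 0.96 | 1.28 |
| Power, signs | 72% / 86% | 43% / 52% |
| Power, CAS | 87% | 64% |

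Power is for a true 1.5-point effect spread evenly over the items, so 1.5 x 5/7 = 1.07 points fall on the signs. The half-width for the pain items is 0.48.

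**The case against.** The strongest reply is that the planned endpoint measures what it claims. The primary outcome is clinical activity by CAS and VISA, Section 3 calls these tools validated, and pain is part of the CAS definition. That stands. A reader might infer that total CAS is an invalid endpoint, or that any CAS benefit would be analgesic. The documents support neither reading: less pain may reflect less inflammation, and the gap concerns interpretation, not the validity of the comparison.

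A reader might also infer that the plan offers no way at all to tell the two apart. That goes too far. VISA names no pain item; proptosis, diplopia and eyelid retraction are evaluated separately; months 6 and 12 are off drug. A difference confined to CAS and to on-drug visits would itself be a warning. These protections are partial, however. The three secondary measures are not CAS items, VISA's items are not listed, and Section 7 gives the late visits no specific role. Although the outcome is defined by both scores, the analysis sentence allows either to be compared.

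Third, over-the-counter analgesic use by controls would tend to shrink the pain effect. That is fair, and such use is unknown. Finally, the signs would be graded with no masking described, so a signs-only score can carry its own bias. That also stands and limits what the addition can prove.

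**Conclusion.** The concern holds as a limit on interpretation. At months 1 and 3, total CAS cannot distinguish pain relief from a change in the inflammatory signs, and Section 7 plans nothing that separates them.

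The size cannot be derived from the documents. Under the assumptions of step 2, with SD 1.5 to 2.0, a pain-only shift makes the CAS test significant 6-7% of the time at 0.18 point and 12-18% at 0.5 point, against a nominal 5%. The 34-54% at 1.0 point should not be read as the expected rate: it takes both pain items to be present in everyone, whereas only 31 of the 99 eligible patterns have both, and even that is a count and not a prevalence. The problem could be negligible or material in this trial. That supports a low-cost supportive addition, not a change of primary endpoint.

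**What to change.** In Section 7:

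- Keep the seven-item CAS comparison as planned, and retain the item scores.
- Pre-specify a supportive between-arm comparison of change from baseline in the five-sign CAS (eyelid erythema, eyelid edema, conjunctival injection, chemosis, caruncular swelling), with estimate and 95% CI at months 1, 3, 6 and 12.
- Show the pain-item difference and its CI beside it.
- State that a month-1 or month-3 CAS difference will be interpreted alongside both estimates and CIs, and will not be described as established reduction of orbital inflammation on the total alone.
- Attach no formal gate and no significance claim to the supportive comparison.
- Where medication history is taken, summarise analgesic use by arm.

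Do not add a cut-off such as pain items making up more than half of the CAS difference. In simulation under the step 3 assumptions, that rule flags about 32-47% of significant results when a genuine 1.5-point effect is split equally between pain and signs. It misses roughly 17-69% when a 0.5-point shift is pain only.

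**Cost.** No new examination is needed, because each item is already graded to assign its point. The planned CAS test loses no power. The five-sign comparison is itself less powerful (step 3), bias from unmasked grading of the signs remains, and the analgesic summary may be incomplete because the document does not say that the medication list is repeated at every visit.
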